## MEDICAL PROTOCOL (HRP-590)

PROTOCOL TITLE: Combining cerebellar tDCS and constraint-induced language therapy in non-fluent aphasia: a novel approach to target discourse

VERSION DATE: 08/09/2023

*of 21.5 hours of participation over the course of the study. If a participant misses an intervention session, we will attempt to make it up during that same week of intervention and reschedule the assessment day. The timing of the assessment day post intervention is critical as tDCS does not appear to have long-lasting effects. The post intervention assessment visit would have to take place within 1-2 days of the last intervention day. If rescheduling is not an option, the total number of intervention sessions attended will be noted in the data. However, if 2 sessions have been missed within either of the intervention periods, the participant will need to be re-enrolled or dropped from the study. Participants will be randomly assigned to receive either the real or sham tDCS first.*

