## 10. Local Number of Participants

10.1. Local Number of Participants to be Consented: *A total of 5 participants will be enrolled with the goal of 3 participants to complete the duration of this pilot study.*

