## 12. Withdrawal of Participants

### 12.1. Withdrawal Circumstances:

*Participants are free to withdraw from participation in the study at any time upon request. An investigator may discontinue or withdraw a participant from the study for the following reasons:*

- *Pregnancy*
- *Significant study non-compliance*
- *If any clinical adverse event (AE) or other medical condition or situation occurs such that continued participation in the study would not be in the best interest of the participant*
- *If the participant meets an exclusion criterion (either newly developed or not previously recognized) that precludes further study participation*

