### 12.2. Withdrawal Procedures:

*If a participant wishes to withdraw or we determine that the participant should withdraw, we will terminate data collection and discuss with the participant the reasons for withdrawal. All data collected up to that point will be used in analysis unless the participant wishes for their data not to be used.*

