## 15. Statistical Considerations

15.1. Data Analysis Plan:

*All data will be de-identified and entered into Excel and SPSS for analysis. Visual analysis will be conducted initially with plotting of descriptive statistics.*

15.2. Power Analysis:

*A literature review of studies measuring the impact of cerebellar tDCS in aphasia did not find usable estimates of variation (SD, SEM, IQR, etc.) for the outcomes of interest. Accordingly, using a standard effect size scale (Cohen's d, scaling the treatment effect size relative to between-participant SD), and a range of plausible within-participant correlations of +0.4 to +0.9, we estimate that enrolling 4 participants will provide 80% power to detect large ( $d=0.9$ ) to very large ( $d=2.3$ ) treatment effect sizes using a two-sided 5% significance level.*

*A post-hoc power analysis will be conducted using the information gathered in the pilot study to determine the sample size needed for a larger study.*

15.3. Statistical Analysis:

*BDAC was consulted regarding the plan for statistical analysis.*

*Based on their recommendations, the following plan was created.*

*Throughout the project, BDAC will be consulted to review this statistical analysis plan and provide additional insight to alternative statistical processes best suited for the data as needed.*

*• The quantitative data for attrition rate and adverse events will be descriptive in nature and will be reported as counts and rates. The*

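### The two-missed-sessions rule lets adherence after randomisation decide who supplies post-treatment outcomes, and undefined re-enrolment leaves the attrition rate open to understatement

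*Combined protocol and SAP*

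**What the plan says.** Section 5.2 randomises the order of conditions: "Participants will be randomly assigned to receive either the real or sham tDCS first". A missed session is to be made up in the same week if possible. If it cannot be, "the total number of intervention sessions attended will be noted in the data" and the participant continues. The consequence changes at two: "if 2 sessions have been missed within either of the intervention periods", "the participant will need to be re-enrolled or dropped from the study". Nothing defines re-enrolment. The documents do not say whether it brings a new identifier, a new randomisation or a new baseline, what happens to first-run data, or whether the second run counts towards the planned number.

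Section 12.1 lists "Significant study non-compliance" among the reasons for which the investigator may withdraw someone. Section 12.2 covers withdrawals decided by either side: "we will terminate data collection and discuss with the participant the reasons for withdrawal". It then keeps the data gathered so far in the analysis unless the participant objects.

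Section 10.1 sets the size: "A total of 5 participants will be enrolled with the goal of 3 participants to complete the duration of this pilot study". Section 15.3 says of the feasibility results: "The quantitative data for attrition rate and adverse events will be descriptive in nature". They are to be given as counts and rates, with no numerator or denominator defined. The same section analyses the primary outcomes with mixed effects generalized linear models that yield a difference-in-differences. No analysis population is named.

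**The concern.** The rule acts on something that happens after randomisation and, for those dropped, stops the outcome from being measured. If missing sessions is related to how a person is doing, those who supply post-treatment scores are a selected group. Section 15.3 intends the pilot's effect size, correlation and variance to feed the next power calculation, so any selection carries forward.

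Re-enrolment raises a separate problem. The person restarting has already had some constraint-induced language therapy, which section 4.1 gives in both conditions, and has already met the discourse stimuli named in section 3.1. The new baseline is therefore not a naive one. Feasibility is a primary aim in section 1.1, and section 2.1 wants the results to help minimise attrition in a larger trial. If a failed run can be followed by a fresh one with no counting rule, the reported retention depends on a choice the plan leaves open.

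**Working it through.** The documents give no rate of missed sessions, so there is no plan figure to reproduce. The only related number is the allowance implied by section 10.1: (5 − 3)/5 = 40% not completing. The power statement in 15.2 is not at issue here.

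**Step 1: what a dropped participant leaves behind.** Table 1 schedules four outcome assessments: visit 2 (baseline 1), visit 9 (after period 1), visit 10 (baseline 2) and visit 17 (after period 2). The treatment effect in 15.3 is (post − pre under real) − (post − pre under sham).

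| Participant | Assessments held | Change scores | Within-person contrast |
|---|---|---|---|
| Completes both periods | 2, 9, 10, 17 | 2 | yes |
| Dropped in period 2 | 2, 9, 10 | 1 | no |
| Dropped in period 1 | 2 | 0 | no |

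The partial records stay in the model. A period-2 drop informs one condition's change. A period-1 drop adds almost nothing to the treatment contrast.

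**Step 2: how often the rule could apply.** Inputs:
- 6 sessions per period (Table 1 and section 5.3);
- threshold of 2 misses in a period (5.2);
- 5 enrolled (10.1);
- q, the chance that a session is missed and not made up. This is an assumption, taken as 5%, 10% and 15%, independent between sessions.

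Per period, p = 1 − (1 − q)^6 − 6q(1 − q)^5. In either of two periods, P = 1 − (1 − p)^2.

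- q = 5%: p = 1 − 0.7351 − 0.2321 = 0.0328; P = 1 − 0.9672² = 6.4%; 5 × P = 0.3 people.
- q = 10%: p = 1 − 0.5314 − 0.3543 = 0.1143; P = 1 − 0.8857² = 21.5%; 5 × P = 1.1 people.
- q = 15%: p = 1 − 0.37715 − 0.39933 = 0.2235; P = 1 − 0.7765² = 39.7%; 5 × P = 2.0 people.

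The chance that at least 3 of 5 never meet the rule (binomial, 5 trials, success probability 1 − P) is 99.8%, 93.0% and 68.8% respectively.

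**Step 3: what undefined re-enrolment does to the attrition rate.** Take 3 people, 2 of whom meet the rule, are re-enrolled once and then finish. That makes 5 enrolments and 3 completers, which would look like section 10.1 met exactly. Attrition is then:
- per enrolment: 2/5 = 40%;
- per person at first attempt: 2/3 = 67%;
- per person at the end: 0/3 = 0%.

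The text allows all three.

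**The case against.** The case on the other side is substantial. Section 12.2 keeps everything collected before withdrawal, and the mixed model can use incomplete participants. Stopping data collection is tied to withdrawal, not to re-enrolment. Even after dropout, section 3.2 seeks the exit survey and section 18.2 continues adverse event recording for 7 or 30 days. Section 15.3 commits to reporting attrition. The miss rates are assumed, and at 5% only 0.3 of 5 people are affected. An attendance threshold is a defensible choice in a pilot this small, and 15.3 itself warns that the models may mainly be descriptive.

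Most of this stands, and it rules out several stronger readings that a reader might draw:
- That adherence decides who is analysed at all. It does not; it decides who supplies post-treatment outcomes and a within-person contrast.
- That data collection ends for everyone who meets the rule. The text supports this only for those dropped.
- That the plan conceals attrition. It does not; the gap is a missing definition.
- That missed sessions reflect poor tolerability, fatigue or lack of benefit. The documents give no cause, and the retention measures in section 11.1 largely concern transport, scheduling and reminders.
- That the rule would apply much more often because section 4.1 gives 12 sessions per condition. Table 1 and section 5.3 give 6, and that contradiction is a separate matter to be reconciled.

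What the objection does not answer is that retained partial data cannot replace an unmeasured post-treatment score, and that neither the survey nor the adverse event record recovers language outcomes.

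**Conclusion.** The point holds in a limited form. Followed as written, the rule loses the post-phase outcome of a dropped participant because of an event after randomisation, and it lets an already exposed person restart with no rule for the first run or for the attrition count. Under the stated assumptions (6 sessions per period, independent misses left after make-up, rates of 5% to 15%), about 6% to 40% of participants would meet the rule, or 0.3 to 2.0 of 5. The direction and size of any bias in the treatment estimate cannot be derived from the documents, because the reasons for missing sessions are unknown. The ambiguity in the attrition rate needs no assumed miss rate: in the example above, the same events give 0%, 40% or 67%. This should be corrected, since attrition is something the pilot exists to measure and the remedy is mostly wording.

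**What to change.** Change the consequences for assessment and analysis only, in sections 5.2, 12.2 and 15.3:

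1. A participant who misses 2 or more sessions in a period, and is willing, still attends the scheduled post-phase assessment and any remaining scheduled assessments. Section 12.2 should separate ending the intervention from ending outcome assessment.
2. Analyse that participant in the randomised sequence, report sessions attended, and count the person as non-adherent in the feasibility results.
3. Flag any post-phase assessment outside the window of 1–2 days in the text of 5.2. Table 1 says within 1 day, so the two should be aligned.
4. If someone is re-enrolled, count the first enrolment as attrition, use its data in the main analysis and report the second run separately. State the numerator and denominator of the attrition rate in 15.3.

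Whether sessions are repeated or the intervention continues is left to the investigator. The 6 versus 12 sessions per condition (Table 1 and 5.3 versus 4.1) must be reconciled separately, because it changes what share of a period two sessions represents.

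The cost is wording plus visits already in the schedule: one (visit 17) after a period-2 trigger, and up to three (visits 9, 10 and 17) after a period-1 trigger, each of 60–75 minutes. After a period-1 trigger, visit 9 alone gives one change score; a within-person contrast also needs the later assessments. The downside is that the estimate may be slightly diluted by people who received fewer sessions.

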### Schedule of Events

Table 1. Schedule of Research Activities.

	Screen / Baselin		Interventio n A or B	Follow- Up 1	Washout	Baselin e 2	Interventio n A or B	Follow- Up 2
Day/Week	Visit 1	Visit 2 Anytime after consent	Visits 3-8 6 total sessions: 3 sessions per week across 2 weeks). Must occur	Visit 9 must occur within 1 day of visit 8	4 weeks	Visit 10 can occur anytime after the 4 week washo ut	Visits 11-16 6 total sessions: 3 sessions per week across 2 weeks Must occur within 5	Visit 17 must occur within 1 day of visit 16
Screen for Eligibility	x							
Consenting Process	x							
Western Aphasia Battery	If needed							

## MEDICAL PROTOCOL (HRP-590)

PROTOCOL TITLE: Combining cerebellar tDCS and constraint-induced language therapy in non-fluent aphasia: a novel approach to target discourse

VERSION DATE: 08/09/2023

Urine Pregnancy Test	Only if within child-bearing years						
Discourse Analysis		X		X		X	X
Verbal Fluency		X		X		X	X
N-back (working memory)		X		X		X	X
Resting state EEG		X		X		X	X
Stroke-Aphasia Quality of Life Survey		X		X		X	X
Adverse Events			X	X			X
Sham OR Real tDCS+CILT			X				X

### Data Collection / Assessment Sessions:

*Participants will be seated comfortably in a chair or in their wheelchair with an adjustable table in front of them. A member of the research team will sit directly across from the participant and present assessment stimuli for the discourse analysis. Discourse analysis will take approximately 15 minutes and will include picture description, story retell and a procedural narration. The verbal fluency test involves naming as many animals as they can in one minute followed by naming as many words starting with /f/ as they can name in one minute. The total time for the verbal fluency task is <5 minutes. N-back will be given using the laboratory computer and takes approximately 10 minutes to complete. These tasks will be videotaped for the purposes of accurate data collection of participant verbal responses. This is necessary for accurate data collection as mild forms of aphasia are harder to assess in real time and may require careful examination of a video. All recordings will be made using Zoom and stored in UMN Box. All temporary files*

## MEDICAL PROTOCOL (HRP-590)

PROTOCOL TITLE: Combining cerebellar tDCS and constraint-induced language therapy in non-fluent aphasia: a novel approach to target discourse

VERSION DATE: 08/09/2023

*will be immediately deleted once uploaded to Box. After the behavioral assessments have been completed, the participant's head will be measured and fit with the EEG cap and electrodes (~15 minutes) and three 2-minute resting state EEG (eyes open) will be done. Finally, the participant will be given the SAQOL questionnaire with as much assistance is needed for reading and/or interpreting the meaning of questions. A visual Likert scale will be provided as a support for language if need be. The participant will be offered breaks between tasks as needed. The research team ran a trial data collection session with one of the members of the research team who provides responses similar to that we would expect of an individual with non-fluent aphasia. The data collection session lasted 75 minutes. One graduate student will be running the EEG portion of the experiment and has been trained and has shown competence in placement of electrode cap and use of the EEG data software. One graduate student will be running the language portion of the experiment and has been trained and has shown competence in the administration and scoring of the discourse, fluency and working memory tasks.*

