## MEDICAL PROTOCOL (HRP-590)

PROTOCOL TITLE: Combining cerebellar tDCS and constraint-induced language therapy in non-fluent aphasia: a novel approach to target discourse

VERSION DATE: 08/09/2023

*to make a peanut butter sandwich". Each task has established standards and a scoring system for responses. Scoring is categorical and includes: accurate and complete =3, accurate and incomplete =2, inaccurate and complete =2, inaccurate and incomplete =1 and absent response =0 (Richardson & Dalton, 2016). Hypothesis: We hypothesize the raw score of each of the discourse measures (picture, story and procedure) will significantly increase after the real tDCS intervention, but not after the sham intervention.*

*2) Verbal Fluency is assessed by asking the participant to name as many animals as they can in one minute and then as many words that start with /f/ as they can in one minute. The tester collects a tally of how many animals and words that begin with /f/ were produced by the participant which is used as a raw score, scaled. If the participant names items that are not within those categories, those responses are not counted in the tally. These tasks are valid and reliable and used throughout aphasia literature.*

*Hypothesis: We hypothesize the raw score of the verbal fluency measures will significantly increase after the real tDCS intervention, but not after the sham intervention.*

*These data will be collected at four points in time:*

- 1) Initial baseline;
- 2) post intervention (A or B);
- 3) Follow-up baseline (after washout period);
- 4) post intervention (A or B)

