### Intervention Sessions:

*Participants will be seated comfortably in a chair with armrests during both the intervention and assessment visits. The assessment and intervention tasks can also be conducted while seated in a wheelchair if need be. Skin where the tDCS electrodes will be placed will be gently cleaned using an alcohol swab and hair will be separated and clipped to allow the electrode to be placed. Two saline-soaked t-DCS sponge electrodes (25 cm^2) will be used. The anode placed over the right cerebellar hemisphere, 1-2cm below the inion and 3-4cm lateral to the inion (Ferrucci et al., 2015; Grimaldi et al., 2016) and the cathode electrode will be placed on the right deltoid region. Electrodes will be kept in place with the neoprene/Velcro head band in the tDCS device kit. The device will be programmed for "real" or "sham" setting for a 20-minute duration using the setting buttons on the device. If the device is programmed for "real" tDCS, the intensity will gradually increase over the first 30-45 seconds to the designated value of 2mA and remain at that setting until it gradually decreases in intensity over the last 30-45 seconds of the 20-minute duration. If "sham" is selected, the gradual ramp up occurs followed by the ramp down. Therefore, no stimulation is provided during sham condition. While the PI is placing the electrodes, the graduate intern will be setting up the behavioral language activity (CILT) for the session. Once the electrodes are in place, the device is programmed and the behavioral activity is set up, the intervention will begin. The tDCS device will be turned on (to either real or sham) and the participant will engage in the*

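### Nothing in the protocol keeps the scorer of the discourse outcome unaware of real or sham condition, although the assessments are already on video and could be scored masked.

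*Combined protocol and SAP*

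**What the plan says.** Section 3.1 makes main concept discourse a primary outcome. The rater places each concept in a category: "Scoring is categorical and includes: accurate and complete =3, accurate and incomplete =2, inaccurate and complete =2, inaccurate and incomplete =1", with 0 for an absent response. The same section states the directional hypothesis that scores rise after real stimulation and not after sham.

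Section 5.2 (Data Collection / Assessment Sessions) assigns the language tasks to one graduate student who "has shown competence in the administration and scoring of the discourse, fluency and working memory tasks". It also provides for video: "These tasks will be videotaped for the purposes of accurate data collection of participant verbal responses". The reason given is that "mild forms of aphasia are harder to assess in real time and may require careful examination of a video".

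Section 5.2 (Intervention Sessions) has the device programmed to real or sham "for a 20-minute duration using the setting buttons on the device". Staff are present in the room: "While the PI is placing the electrodes, the graduate intern will be setting up the behavioral language activity (CILT) for the session". Section 4.1 likewise places a speech-language pathologist and a graduate student assistant at the therapy.

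Section 5.2 also says that the order of conditions is assigned at random. The only coding described is the participant code in Section 15.4. No section mentions blinding or masking of the assessor or scorer, recoding of recordings, or the order in which they are scored.

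**The concern.** Discourse scoring rests on judgement, is done by someone on a small team with a stated expectation, and is compared between two conditions whose setting is chosen by hand at the session. In a two-period crossover, one sight of the setting in either period reveals the condition in both.

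The sham ramp acts on the participant's side of the comparison. It does nothing about the person who assigns the scores.

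Section 15.3 describes the pilot's estimates as unobtainable elsewhere and intends to use the treatment effect size in the next power calculation. If scoring favoured real stimulation, that effect would be overstated and the larger trial planned too small.

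**Working it through.** **Inputs.** Four scored visits per participant (Section 3.1). Model with treatment, period, sequence, pre-post time point and the treatment by time-point interaction (Section 15.3). n = 4, two-sided 5%, 80% power, within-participant correlation ρ from 0.4 to 0.9, d from 0.9 to 2.3 in between-participant SDs (Section 15.2). Five enrolled with a goal of three completers (Section 10.1). The scorer shift is not in the documents; 0.1 to 0.3 SD is an assumption.

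**1. The plan's own figure.** A paired t-test with n = 4 (3 df) reaches 80% power at a standardised mean difference of 2.128. With d = 2.128 × √(2(1 − ρ)):
- ρ = 0.9: 2.128 × √0.2 = 0.95
- ρ = 0.4: 2.128 × √1.2 = 2.33

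This agrees with the stated 0.9 to 2.3, the ends being rounded down. The figure serves here only as a yardstick.

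**2. What a scorer shift does to the estimate.** Let s be the amount that the scorer adds at each visit. The bias is

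(s at post-real − s at pre-real) − (s at post-sham − s at pre-sham).

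- Scorer knows only pre or post and adds c to every post score: (c − 0) − (c − 0) = 0. If the addition differs between the first and second post visit, it still averages out over the randomised order in expectation.
- Scorer knows the condition and adds b at post-real only: (b − 0) − (0 − 0) = b. This sits exactly in the treatment by time-point cell, so the period, sequence and baseline terms cannot separate it from a treatment effect.

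**3. Size under the assumed shift.**

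| Assumed b (SD) | Share of d = 0.9 | Share of d = 2.3 |
|---|---|---|
| 0.1 | 0.1/0.9 = 11% | 0.1/2.3 = 4% |
| 0.2 | 0.2/0.9 = 22% | 0.2/2.3 = 9% |
| 0.3 | 0.3/0.9 = 33% | 0.3/2.3 = 13% |

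**4. Chance of a significant result when the true effect is zero** (n = 4, noncentral t with 3 df, nominal 5%). The standardised bias is b/√(2(1 − ρ)) for the simple paired comparison behind the power statement. It is b/√(4(1 − ρ)) for a difference in differences, assuming equal correlation across the four visits.

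| b | Paired, ρ = 0.9 | Paired, ρ = 0.4 | Diff-in-diff, ρ = 0.9 | Diff-in-diff, ρ = 0.4 |
|---|---|---|---|---|
| 0.1 | 6.2% | 5.2% | 5.6% | 5.1% |
| 0.2 | 9.9% | 5.8% | 7.4% | 5.4% |
| 0.3 | 16.0% | 6.8% | 10.5% | 5.9% |

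With so few participants the effect on the test is small to moderate. The bias in the estimate is b in every column.

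**5. Is masked scoring practicable?** At most 5 × 4 = 20 assessment visits, or 3 × 4 = 12 if three complete. In Section 5.2 the language tasks come before the EEG cap is fitted, and the schedule of events shows no stimulation at assessment visits, so the set-up described does not itself reveal the condition on the recording.

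**The case against.** The strongest reply is that this is silence, not a documented fault. Section 5.2 does not say who presses the device buttons, whether a student sees the setting, how video files are named, or whether the intern at the therapy is the student who scores. The standard operating procedures and data form are cited but are not part of the documents and might cover scoring. All of this stands. A reader might infer that the scorer knows the condition; the documents do not show it.

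A reader might also infer that knowing the time point biases the treatment comparison. Step 2 shows that a common post-visit shift cancels, so only knowledge of condition matters.

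Section 3.1 refers to established standards for each discourse task, and two of its categories share the score 2, so some disagreements change nothing. That limits the room for judgement without removing it. Verbal fluency is a tally of in-category words and is far less exposed; the argument does not carry over to it.

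Finally, this is a small pilot with feasibility among its primary aims, and Section 15.3 concedes that its repeated-measures and correlation analyses may not tell much. That weakens the concern about significance tests. It does not answer the concern about the effect estimate, which the same section carries forward.

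**Conclusion.** The point holds as a missing safeguard. The protocol leaves open that the person scoring a judgement-based primary outcome knows the condition, and it does not use the video it already has to close that gap.

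If the scorer does know, a preference for post-real visits enters the difference-in-differences estimate one for one. The size cannot be derived from the documents. The range of 11–33% (against d = 0.9) or 4–13% (against d = 2.3) is the assumed 0.1 to 0.3 SD divided by the two ends of the plan's range; it is not an estimate of actual bias. The conclusion is confined to discourse and to knowledge of condition. The change is worth making because it is cheap and protects the figure most likely to be reused.

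**What to change.** In Section 5.2, state that:
- the discourse score taken from the existing video is the analysed score, with the live score kept as a check;
- recordings carry random codes that hide visit and condition;
- they are scored in shuffled order; shuffling within a participant after that participant's last visit is enough, so scoring need not wait for the end of enrolment;
- the scorer is an existing team member, trained under the study's operating procedures, who did not attend that participant's intervention sessions and cannot see the allocation;
- scores are locked before the code list is opened.

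Section 15.4 gives all approved staff access to the study files in Box, so the recording code list and the allocation need a folder closed to the scorer.

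Cost: scores arrive later, and student roles must be kept apart. The student who ran the visits could recognise the recordings, so a second existing team member may need brief training in main concept scoring. Participants do nothing extra, and the sample size and analysis model are unchanged. Verbal fluency need not be included.
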